## Analysis of all treatment emergent serious adverse event(s)

- All serious TEAEs by primary SOC, HLGT, HLT, and PT;
- All serious TEAEs regardless of relationship in one column and, in the same table a second column with TEAEs related to IMP according to Investigator's opinion, by primary SOC, HLGT, HLT, and PT;
- The event rate per patient-year will be provided for all serious TEAEs by SOC and PT;
- All SAEs will be listed.

#### Analysis of all treatment-emergent adverse event(s) leading to treatment discontinuation

All TEAEs leading to treatment discontinuation, by primary SOC, HLGT, HLT, and PT.

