### 10.3.2 Permanent treatment discontinuation with investigational medicinal product(s)

Permanent treatment discontinuation is any treatment discontinuation associated with the definitive decision from the Investigator or the patient not to re-expose the patient to the IMP at any time. Patient withdrawal from the study treatment or study should be avoided as much as possible.

This section is not applicable for patients who are randomized to usual care for whom no additional LMT is added.

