#### 11.4.3.1 Adverse events

Adverse event incidence tables will present by SOC (sorted by internationally agreed order), HLGT, HLT and PT sorted in alphabetical order for each treatment group, the number (n) and percentage (%) of patients experiencing an AE. Multiple occurrences of the same event in the same patient will be counted only once in the tables within a treatment phase. The denominator for computation of percentages is the safety population within each treatment group.

Adverse event incidence table will be provided by treatment group for all types of TEAEs: all TEAEs, all treatment-emergent AESI (defined with a PT or a prespecified grouping), all treatment-emergent SAEs and all TEAEs leading to permanent treatment discontinuation.

If any clinically significant signal is detected and needs further characterization or for AE of clinical interest, exploration of time to onset will be performed for these selected TEAEs as described below to account for the differential exposure time in all patients.

Selected TEAEs will be also analyzed using time-to-event approach (Kaplan-Meier methodology). Time to the first occurrence of the event will be calculated (only the first event will be counted), with the origin date being the date of the first dose of open-label IMP for patients receiving an additional IMP (alirocumab or usual care) or the date of the randomization for patients not receiving an IMP (statins only). Patients without any event will be censored at the end of the TEAE period. Incidence rates at 6 months will be presented and Kaplan-Meier curves will be provided.

Death: The following deaths summaries will be generated:

- Number (%) of patients who died by study period (TEAE, on-study, post-study) summarized on the safety population by treatment received
- Death in non-randomized patients or randomized and not treated patients
- TEAE leading to death (death as an outcome on the AE CRF page as reported by the Investigator) by primary SOC, HLGT, HLT and PT showing number (%) of patients sorted by internationally agreed order of SOC and alphabetic order of HLGT, HLT, and PT.

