#### 2.2 DISPOSITION OF PATIENTS

This section describes patient disposition for both patient study status and the patient analysis populations.

Screened patients are defined as any patients who signed the informed consent.

Randomized patients consist of all screened patients who are recorded in the IVRS/IWRS database (if randomized to usual care) and with a treatment kit allocated (if randomized to alirocumab), regardless of whether the treatment kit was used or not. Patients treated without being randomized or treated with a treatment kit before the randomization will not be considered as randomized and will not be included in any analysis population. The safety experience of patients treated and not randomized will be reported separately and these patients will not be in the safety population.

For any patient randomized more than once, only the data associated with the first randomization will be used in any analysis population. The safety experience associated with any later randomization will be assessed separately.

For patient study status, the total number of patients in each of the following categories will be presented by randomization stratum (for strata with at least 10% of patients) and in the pooled data in the clinical study report using a flowchart diagram or summary table:

Property of the Sanofi Group - strictly confidential

- Version number: Final
- Screened patients;
- Screen failure patients and reasons for screen failure;
- Non-randomized but treated patients;
- Randomized patients;
- Randomized but not treated patients and reason for not treated (not applicable for patients randomized to usual care arm without intent to prescribe an additional LMT);
- Randomized and treated patients;
- Patients who completed the study treatment period as per protocol;
- Patients who discontinued the study treatment and main reason for permanent treatment discontinuation (not applicable for patients randomized to usual care arm without intent to prescribe an additional LMT);
- Patients who completed the study period as per protocol;
- Patients who discontinued the study and main reason for study discontinuation;
- Status at last study contact.

For all categories of patients (except for the screened and non-randomized categories) percentages will be calculated using the number of randomized patients as the denominator.

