# 2.3.2 Safety population

The safety population considered for safety analyses will be the randomized population who did actually receive at least one dose or part of a dose of the open-label alirocumab and all patients randomized to usual care.

Patients will be analyzed according to the treatment actually received (usual care or alirocumab).

The safety analysis will focus on the TEAE period defined in Section 2.1.4.

In addition:

- Non-randomized but treated patients or patients treated before the randomization will not be part of the safety population, but their safety data will be presented separately;
- Randomized patients for whom it is unclear whether they took the study medication will be included in the safety population as randomized;
- For patients receiving more than one study treatment during the trial, the treatment group allocation for as-treated analysis will be the one to which the patient was treated with the longest duration.

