#### 2.4.5 Analyses of safety data

The summary of safety results will be presented by actual treatment group. Summaries will be descriptive in nature. Safety analyses will be performed overall and by actual stratum defined by the actually received treatment (only for strata with at least 10% of patients).

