#### 2.4.5.1 Analyses of adverse events

#### **Generalities**

The primary focus of AEs reporting will be on TEAEs. Pre-treatment and post-treatment AEs will be described separately.

If an AE date/time of onset (occurrence, worsening, or becoming serious) is incomplete, an imputation algorithm will be used to classify the AE as pre-treatment, treatment-emergent, or post-treatment. The algorithm for imputing date/time of onset will be conservative and will classify an AE as treatment emergent unless there is definitive information to determine it is pre-treatment or post-treatment. Details on classification of AEs with missing or partial onset dates are provided in Section 2.5.2.

Adverse event incidence tables will present, the number (n) and percentage (%) of patients experiencing an AE by SOC, HLGT (when applicable), HLT (when applicable), and PT. Multiple occurrences of the same event in the same patient will be counted only once in the tables within a treatment phase. The denominator for computation of percentages is the safety population within each treatment group.

Sorting within tables ensures the same presentation for the set of all AEs within the observation period (pre-treatment, treatment-emergent, and post-treatment). For that purpose, the table of all TEAEs presented by SOC and PT sorted by the internationally agreed SOC order and decreasing frequency of PTs within SOCs (in the alirocumab group) will define the presentation order for all other tables unless otherwise specified. The tables of AEs by SOC, HLGT, HLT, and PT will be sorted by the internationally agreed SOC order and the other levels (HLGT, HLT, PT) will be presented in alphabetical order, unless otherwise specified.

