#### Analysis of all treatment-emergent adverse events

The following TEAEs summaries will be generated for the safety population.

- Overview of TEAEs, summarizing number (%) of patients with any
  - o TEAE;
  - Serious TEAE;

- o TEAE leading to death;
- TEAE leading to permanent treatment discontinuation (patients in usual care treatment arm with no additional LMT are excluded from denominator).
- Number (%) of patients experiencing TEAEs by primary SOC, HLGT, HLT, and PT sorted by the international agreed SOC order and by alphabetical order for the other levels (HLGT, HLT, PT);
- Number (%) of patients experiencing common TEAE(s) presented by primary SOC, HLT and PT (HLT incidence ≥2 % in any treatment group), sorted by internationally agreed SOC order and by alphabetic order for the other levels (HLT and PT);
- Number (%) of patients experiencing TEAEs by primary SOC and PT, sorted by the internationally agreed SOC order and by decreasing incidence of PTs within each SOC (in the alirocumab group). This sorting order will be applied to all other tables of TEAEs by SOC and PT, unless otherwise specified;
- All TEAEs regardless of relationship in one column and, in the same table a second column with TEAEs related to IMP according to Investigator's opinion by primary SOC, HLGT, HLT and PT;
- All TEAEs by maximal intensity (i.e., mild, moderate or severe), presented by primary SOC and PT, sorted by the sorting order defined above;
- The event rate per patient-year (the number of patients with an event in question divided by total patient-years) will be provided for all TEAEs by SOC and PT. For a patient with event, patient year is censored at time of first event; for patient without event, it corresponds to length of TEAE period;
- Kaplan-Meier curves will be provided, when appropriate, for time from first dose of openlabel IMP to the first occurrence of selected TEAEs as well as incidence rates at the time of analysis (Week 24 for the first analysis, Week 32 for the final analysis). Hazard ratio versus usual care group and corresponding 95% CI will be given. Patients without any event will be censored at the end of the TEAE period. Selected TEAEs will be local injection site reactions, general allergic reactions, neurocognitive events, hepatic disorders and TEAE related to any clinically significant signal that needs further characterization.

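### First-step patient-year AE rates count time after the cut-off as event-free, and the detailed table of TEAEs leading to discontinuation does not repeat the overview's denominator exclusion

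*SAP*

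**What the plan says.** **First-step person-time.** SAP section 3 sets the cut-off at the last Week 24 visit. AEs that start, worsen or become serious after it are left out for all patients. Patients with no end-of-treatment visit by then are treated as ongoing, and their TEAE period stops at the cut-off. Nothing is said about the TEAE period of patients who have had the visit. SAP 2.1.4 runs that period to 70 days after the last injection (alirocumab), or to 70 days after the last intake or last on-site visit with a cap at Day 225 (usual care). The patient-year rate in SAP 2.4.5.1 gives a patient without an event the whole TEAE period as time at risk.

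**Discontinuation table.** SAP 2.4.5.1 (Generalities) sets the default for AE tables: "The denominator for computation of percentages is the safety population within each treatment group". SAP 2.3.2 defines that population as patients who received "at least one dose or part of a dose of the open-label alirocumab and all patients randomized to usual care". In the overview of TEAEs, the row for permanent treatment discontinuation carries an exception: "patients in usual care treatment arm with no additional LMT are excluded from denominator". The overview of AESIs and hepatic disorders repeats it. The breakdown by MedDRA level, "All TEAEs leading to treatment discontinuation, by primary SOC, HLGT, HLT, and PT", carries none. Protocol 11.4.3.1 likewise lists "all TEAEs leading to permanent treatment discontinuation" among tables that use the safety-population denominator.

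**The concern.** In a patient-year rate, events and time at risk must end on the same date. Here the events stop at the cut-off for everyone, while the clock runs on for nearly everyone, because by the date of the last Week 24 visit almost all patients have had their own end-of-treatment visit. The first step is meant for scientific communication (Protocol 6.3 and 11.5), so these could be the first rates made public.

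For the discontinuation table, no-LMT usual-care patients cannot enter the numerator. Protocol 10.3.2 says of permanent discontinuation: "This section is not applicable for patients who are randomized to usual care for whom no additional LMT is added". Keeping them in the denominator dilutes the usual-care percentages and leaves alirocumab's unchanged. The overview row removes this dilution and the detailed table does not.

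**Working it through.** **Plan figures reproduced.** The last injection is at Week 22, which is Day 22 × 7 + 1 = 155. Adding 70 days gives Day 225, and Week 32 is Day 32 × 7 + 1 = 225, as the flow chart states. For usual care, min(169 + 70, 225) = 225. Randomizing 420 patients 2:1 gives 280 and 140, as stated.

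**Part 1: first-step rates**

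1. On the planned schedule the Week 24 visit is Day 169 and the TEAE period ends on Day 225 in both arms. The unobserved time is at most 225 - 169 = 56 days per completer.
2. The visit and injection windows move this a little. With the visit at Day 166, usual care has up to 225 - 166 = 59 days. Alirocumab has no Day 225 cap: a last injection 3 days late gives 158 + 70 - 166 = 62 days, and 7 days late gives 162 + 70 - 166 = 66 days.
3. The documents do not give the accrual time. Assume uniform accrual over A weeks. A share 56/(7A) of patients is affected, and the mean unobserved time over all patients is 56²/(2 × 7A) days. Dividing by 225 gives the share of time at risk that was not observed. For infrequent events, rate shown = true rate × (1 - share).

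| A (weeks, assumed) | Patients affected | Mean unobserved days | Share of time at risk | True 20 per 100 patient-years shows as |
|---|---|---|---|---|
| 20 | 40% | 11.2 | 5.0% | 19.0 |
| 26 | 31% | 8.6 | 3.8% | 19.2 |
| 52 | 15% | 4.3 | 1.9% | 19.6 |
| 78 | 10% | 2.9 | 1.3% | 19.7 |

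4. A simulation (420 patients, 4,000 runs, visits and last injections spread over ±3 days) gave shares of 4.7%, 3.6%, 1.9% and 1.3%. The two arms agreed to about 0.01 percentage points. Faster accrual enlarges the effect: 12 weeks would give 8.3%.

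**Part 2: discontinuation table**

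1. Let s be the share of usual-care patients with no added LMT. The documents do not give it, so it is assumed here.
2. For the same count, the percentage on the full arm equals (1 - s) times the percentage on the overview row's base.
3. Illustration with 5 of 140 usual-care patients. The full arm gives 5/140 = 3.6%.

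| s (assumed) | Base after exclusion | 5 patients as a percentage | Factor (1 - s) |
|---|---|---|---|
| 5% | 133 | 3.8% | 0.95 |
| 10% | 126 | 4.0% | 0.90 |
| 20% | 112 | 4.5% | 0.80 |
| 30% | 98 | 5.1% | 0.70 |

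**The case against.** **First step.** It is conditional. Protocol 6.3 and 11.5 and SAP section 3 all allow for it not being needed, and then the problem does not arise. SAP section 3 also limits first-step safety data to the cut-off for everyone, so a careful programmer might stop all follow-up there. That stands as a sensible reading, but it is not what the rules say. The end of the TEAE period is calculated from a last-dose or last-visit date already known, so a data cut does not shorten it, and truncation is written for ongoing patients only. A reader might also infer that the first-step Kaplan-Meier incidence is biased. The SAP reads it at Week 24, and for completers censoring dates after that day do not change the estimate at that day.

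**Discontinuation table.** The bullet names no denominator, and the omitted parenthesis may be a drafting slip. A reader might infer that the report will certainly print two usual-care percentages for one count. The documents do not support that: the overview is an any-event row, the other table is a breakdown by term, and no text specifies an overall row in it. What stands is that the two outputs are on different bases under the default rule, and that any overall row would disagree with the overview. Keeping the full safety population is itself defensible, since every AE table then shares one N and the pooled arms keep the same stratum mix. Either base is workable if it is labelled. The by-stratum tables help too ("Safety analyses will be performed overall and by actual stratum defined by the actually received treatment"), but only for strata with at least 10% of patients.

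**Disposition.** A reader might also see a contradiction in SAP 2.2. There is none: the treatment-discontinuation row is already marked "not applicable for patients randomized to usual care arm without intent to prescribe an additional LMT". Saying whether these patients are in that row's denominator and in the risk set of the discontinuation curve would be an optional clarification.

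**Conclusion.** Both parts hold, and both are minor. Part 1 is the main one: as written, the rules give first-step patient-year rates that are too low, by about 1.3% to 5.0% for assumed uniform accrual of 78 to 20 weeks. The effect is nearly equal in the two arms, so it does not favour alirocumab. The rates are descriptive and are replaced by the Week 32 update.

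Part 2 rests on the general denominator rule together with the missing exception, not on an explicit instruction. It lowers only the usual-care percentages in the detailed table, by a factor (1 - s). Its size cannot be fixed without the no-LMT share.

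The primary analysis and the testing hierarchy are unaffected by either part.

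**What to change.** 1. Add one sentence to SAP section 3: at the first step, the TEAE period and time at risk of every patient end at the earlier of the defined TEAE-period end and the cut-off date.
2. In SAP 2.4.5.1, apply the overview row's exclusion to the detailed table of TEAEs leading to treatment discontinuation, and print the denominator in its header or a footnote.
3. Keep the by-stratum display. After the exclusion the pooled arms differ in stratum mix, because alirocumab keeps its no-LMT stratum and usual care does not.
4. Optionally, state in SAP 2.2 that no-LMT usual-care patients are outside the denominator of the treatment-discontinuation row and the risk set of the matching curve.

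The cost is a few SAP sentences and minor programming, with no new data. The one drawback is the stratum mismatch in item 3.

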## Analysis of groupings of adverse events including selected adverse events of special interest

- All grouping of TEAEs including AESI as listed in Section 2.1.4.1 will be analyzed using selections defined in Section 2.1.4.1. They will be presented by SOC, HLGT and PT. The summaries will be sorted by decreasing incidence of PT within each SOC and HLGT (in the alirocumab group).
- Overview of AESI and grouping of hepatic disorders will be presented summarizing number (%) of patients with any
  - o AE;
  - o TEAE;
  - TEAE leading to death;
  - TEAE leading to permanent treatment discontinuation (patients in usual care treatment arm with no additional LMT are excluded from denominator).
- In addition, the following variables will be tabulated for the local injection site reactions TEAEs:
  - Highest intensity of the event (mild, moderate, severe);
  - Mean duration (days);
  - o Number of events divided by the number of open-label treatment injections received;
  - o Time from first open-label treatment injection to first injection site reaction;
  - o Number of open-label IMP injections up to the first injection site reaction;
  - Description of the highest intensity of each symptom recorded in the specific e-CRF page with tables and bar chart.
- Besides, description of symptoms and possible etiologies for general allergic reaction TEAE reported by Investigator will be presented.

#### Analysis of pre-treatment and post-treatment adverse events

- All pre-treatment AEs by primary SOC and PT, sorted by the internationally agreed SOC order and decreasing incidence of PTs (in the alirocumab group) within each SOC;
- All pre-treatment AEs leading to treatment discontinuation by primary SOC and PT, sorted by the sorting order defined above;
- All post-treatment AEs by primary SOC and PT, sorted by the internationally agreed SOC order and decreasing incidence of PTs (in the alirocumab group) within each SOC;
- All post-treatment SAEs by primary SOC and PT, sorted by the sorting order defined above.

Subgroups of patients with 2 consecutive LDL-C <25 mg/dL or 2 consecutive LDL-C <15 mg/dL  $\,$ 

26-Apr-2017

If applicable, similar summaries of TEAEs as those described above will be also provided on the safety subgroup population of patients with 2 consecutive results, spaced out by at least 21 days, of calculated LDL-C <25 mg/dL (<0.65 mmol/L) (respectively calculated LDL-C <15 mg/dL, i.e., <0.39 mmol/L). Only TEAE for which it will be confirmed or unclear that they occurred, worsened or became serious the day or after the first level of

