#### **ASSESSMENT SCHEDULE**

**V1**: (Week -3, [Day -21 to -8]): screening, alirocumab (placebo IMP) injection training\*, safety.

**V2**: (Week 0 [Day 1 + 3]): baseline, randomization, first administration with open label alirocumab (if the patient is randomized to alirocumab) or initiation of usual care (if the patient is randomized to the usual care (non-alirocumab) arm), and as per the prescription of the Investigator), safety. Patients will have the option to self-inject/inject a second time with placebo after the first screening injection training and before randomization. For patients randomized to alirocumab, additional training can be performed with open

label alirocumab at this visit.

V3: (Week 4[Day 29 ±7 days]): telephone contact.

V4: (Week 8 [Day 57 ±3 days]); V6: (Week 20 [Day 141 ±7 days]): Efficacy and safety assessment parameters.

**V5**: (Week 12 [Day 85  $\pm$ 3 days]): Second allocation of open label alirocumab if randomized to alirocumab or prescription for usual care treatment (IMP) if randomized to usual care (as applicable), efficacy, and safety assessment parameters.

**V7**: (Week 24 [Day 169  $\pm$ 3 days]): End of open label treatment visit, efficacy, and safety assessment parameters.

**V8**: (Week 32 [Day 225 ±7 days]): telephone contact, safety assessment.

\*In case a designated person plans to inject the patient but is not present at the time of the screening visit, a dedicated training visit may be scheduled during the screening period prior to the randomization visit or training can be performed at the randomization visit prior to study drug administration.

Note: If one visit is changed, the next visit should take place according to the original schedule.

Patients who prematurely discontinue treatment should be followed as scheduled.

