# Laboratory tests

The laboratory data are collected in accordance with the study schedule and the details provided in the Study Flow Chart (Section 1.2).

- Hematology: all visits except Weeks 4 and 20; may be performed at Week 0 as applicable and based on the clinical discretion of the Investigator
- Chemistry: all visits except Weeks 4 and 20; may be performed at Week 0 as applicable and based on the clinical discretion of the Investigator, except for plasma glucose which should be performed at Week 0 for all patients
- HbA1c: screening and Weeks 0, 12, and 24
- Lipid panel: screening and Weeks 0, 8, 12, 20, and 24
- Measured LDL-C via beta quantification: screening and Weeks 0, 8, 12, 20, and 24
- Other lipid assessments (Apo B, Apo A-1, Apo C-III, lipid subfractions by NMR spectroscopy, Lp[a]): Weeks 0, 8, 12, 20, and 24
- Liver panel: all visits except Weeks 4 and 20; may be performed at Week 0 as applicable and based on the clinical discretion of the Investigator. In case of total bilirubin values above the normal range, differentiation into conjugated and non-conjugated bilirubin will occur automatically
- CPK: all visits except Weeks 4 and 20; may be performed at Week 0 as applicable and based on the clinical discretion of the Investigator.

- Hepatitis B surface antigen: screening only.
- Hepatitis C antibody: at screening and Week 24; in case of ALT increase during the study, hepatitis C antibody should be determined. If Hepatitis C antibody is positive during the study, reflexive testing should be performed.
- Pregnancy testing (in women of childbearing potential only): serum pregnancy test at screening only. Urine pregnancy test at Weeks 0 and 24.
- Thyroid stimulating hormone: screening only for patients who are taking thyroid hormone replacement.
- PCSK9 levels will be measured at Weeks 0, Week 12, and Week 24.
- Anti-alirocumab antibodies: Weeks 0, Week 12, and Week 24.

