# 10.3.4 Handling of patients after permanent treatment discontinuation

Patients will be followed-up according to the study procedures as specified in this protocol up to the scheduled date of study completion, or up to recovery or stabilization of any AE to be followed-up as specified in this protocol, whichever comes last. This means that patients who prematurely discontinue study treatment (regardless of the reason) should still continue the study and undergo all visits and procedures as described in Section 1.2 with the exception of study treatment administration and its associated procedures. If possible, and after the permanent discontinuation of treatment, the patients will be assessed using the procedure normally planned for the end of open-label treatment visit (this should take place within 5 days of treatment discontinuation, if possible) and then resume the original study schedule until end of study.

If after treatment discontinuation, the patient refuses to resume the original study schedule until the end of the study, then if possible, the patient should undergo an unscheduled visit with assessments normally planned at the end of open-label treatment visit (it should take place within 5 days of treatment discontinuation, if possible). The patient, at a minimum, should then be followed-up for at least 10 weeks from the last administration of IMP or until recovery or stabilization of any AE as specified in this protocol, whichever comes last. A final end of study phone visit will take place 10 weeks after the premature discontinuation.

All cases of permanent treatment discontinuation should be recorded by the Investigator in the appropriate pages of the CRF when considered as confirmed. IVRS/IWRS should be notified when a patient prematurely discontinues study treatment. In the medical record, at least the date of the withdrawal and the reason should be documented.

18-Nov-2015 Version number: 1

This section is not applicable for patients who are randomized to usual care for whom no additional LMT is added.

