#### 2.4.5.2 Deaths

The following summaries of deaths will be generated for the safety population.

LDL-C <25 mg/dL (respectively <15 mg/dL) will be considered.

- Number (%) of patients who died by study period (on-study, on-treatment, post-study);
- Deaths in non-randomized patients or randomized but not treated patients
- Treatment-emergent AEs leading to death (death as an outcome on the AE e-CRF page as reported by the Investigator) by primary SOC and PT showing number (%) of patients sorted by internationally agreed SOC order, with PT presented in alphabetical order within each SOC. TEAE leading to death are TEAE that led to death regardless of timing of death in relation to IMP injection (i.e., death occurring in the TEAE period or during the post-treatment period).
- All deaths will be listed, with reason.

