#### 2.5.4 Unscheduled visits

For efficacy, safety laboratory data, or vital signs, unscheduled visit measurements may be used to provide a measurement for a time point, a baseline, a last or a worst value, if appropriate according to their definitions. The measurements may also be used to determine abnormal/PCSA.

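### The very-low-LDL-C safety subgroups require two low values but count adverse events from the first, so events that end follow-up between the two are lost and their rates read too low

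*SAP*

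**What the plan says.** SAP 2.4.5.1 (the paragraph on two consecutive LDL-C values below 25 or 15 mg/dL) repeats the adverse event summaries, if applicable, in "patients with 2 consecutive results, spaced out by at least 21 days, of calculated LDL-C <25 mg/dL", and likewise for 15 mg/dL. A TEAE is included when it is confirmed or unclear that "they occurred, worsened or became serious the day or after the first level of" low LDL-C. In the text version the sentence ends under 2.4.5.2, Deaths: "LDL-C <25 mg/dL (respectively <15 mg/dL) will be considered".

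The summaries to be repeated include fatal TEAEs, TEAEs leading to permanent discontinuation, and event rates per patient-year. For a patient without the event, patient-years are the full TEAE period. No landmark, time-dependent handling or separate start of person-time is given for these subgroups.

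On sampling, Protocol Section 10 (Laboratory tests) has "Lipid panel: screening and Weeks 0, 8, 12, 20, and 24". Protocol 10.3.4 states that "patients who prematurely discontinue study treatment (regardless of the reason) should still continue the study and undergo all visits and procedures", apart from study treatment and its associated procedures. It also asks for an early end-of-treatment assessment ("this should take place within 5 days of treatment discontinuation, if possible").

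**The concern.** Membership is decided by a later value, while counting starts at an earlier one. To be in the subgroup, a patient must have survived and stayed under observation from the first low value to the second. That stretch is counted, but by construction it cannot contain a death or a study withdrawal. This is immortal time, and it lowers the rates of the outcomes that end follow-up.

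The bias runs in one direction, towards a better-looking safety profile at very low LDL-C. The question is a live one here: Protocol Section 4 reports cataracts in 2.1% of alirocumab patients with two consecutive LDL-C values below 25 mg/dL, against 0.6% of alirocumab patients without them.

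**Working it through.** The documents give no event figure for these subgroups, so there is nothing to reproduce. The check is date arithmetic plus a simple hazard model.

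**Inputs**
- Scheduled post-baseline lipid days: 57, 85, 141 and 169 (Weeks 8, 12, 20, 24; protocol flow chart).
- Visit windows: ±3 days, except ±7 at Week 20 (protocol assessment schedule: "Week 8 [Day 57 ±3 days]); V6: (Week 20 [Day 141 ±7 days").
- Last planned injection: Week 22, Day 1 + 22 × 7 = Day 155 (Protocol 6.1).
- End of the TEAE period for a completer: Day 155 + 70 = Day 225 (SAP 2.1.4).

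**Gap and time at risk.** Gap g = second day − first day. Time at risk T = 225 − first day.

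| Pair of values | g (days) | T (days) | g/T | 1 − g/T |
|---|---|---|---|---|
| Weeks 8, 12 | 85 − 57 = 28 | 168 | 17% | 0.83 |
| Weeks 12, 20 | 141 − 85 = 56 | 140 | 40% | 0.60 |
| Weeks 20, 24 | 169 − 141 = 28 | 84 | 33% | 0.67 |

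With the visit windows and the 21-day rule, the gaps run 22–34, 46–66 and 21–38 days. If an intermediate value is missing and the next available result is taken as consecutive, the gap can reach 84 days (Weeks 8 to 20 or 12 to 24) or 112 days (Weeks 8 to 24).

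**Events that end follow-up (death, withdrawal).** Take a constant hazard with true cumulative risk c over T, so h = −ln(1 − c)/T. Subgroup members can have the event only after the second value, so the observed risk is 1 − exp(−h(T − g)). With c = 2% (assumed) this gives 1.67%, 1.20% and 1.34%. The ratios to the true risk, about 0.83, 0.60 and 0.67, barely change for c = 1% or 5%.

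**Events that end treatment only.** Sampling continues, so the patient is lost only if LDL-C has risen above the threshold by the second sample. As an assumption, borrow the 21-day carry-over that SAP 2.4.4.1.3 uses for non-HDL-C. Injections are planned every 14 days (Days 1, 15, …, 155).
- Weeks 8–12: stopping on Days 57–70 leaves Day 57 as the last dose, and 85 − 57 = 28 > 21. That is 14 days lost. From Day 71, 85 − 71 = 14 ≤ 21, so the patient is retained.
- Weeks 12–20: stopping on Days 85–126 leaves Day 113 at the latest, and 141 − 113 = 28 > 21. That is 42 days lost.
- Weeks 20–24: stopping on Days 141–154 leaves Day 141, and 169 − 141 = 28 > 21. That is 14 days lost.

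As shares of T: 14/168 = 8%, 42/140 = 30% and 14/84 = 17%.

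**Patient-years.** If the denominator is the whole TEAE period, time before the first low value is included: 57 − 1 = 56, 85 − 1 = 84 or 141 − 1 = 140 days, in which no event can count. For event-free completers the relevant time is 168, 140 or 84 of 225 − 1 = 224 days, that is 0.75, 0.625 or 0.375 of the denominator. This dilutes patient-year rates for every type of event, separately from the gap.

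**The case against.** The strongest reply is that stopping treatment does not remove a patient. Protocol 10.3.4 keeps such patients in the study with all visits, the early assessment can supply a second value if it falls at least 21 days after the first, and SAP 2.5.4 says "unscheduled visit measurements may be used to provide a measurement for a time point". This stands. A reader might infer that any treatment-ending event drops out and that the 0.83, 0.60 and 0.67 ratios apply to it. The documents do not support that: those ratios belong to events that end follow-up.

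A reader might also infer that four to eight weeks are guaranteed free of such events. Only 21 days are fixed by rule; the 28 and 56 days are nominal.

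Nor are all serious or fatal TEAEs understated. Serious events that leave the patient under observation are counted from the first low value. A TEAE that starts in the gap and proves fatal after the second value is counted too, because SAP 2.4.5.2 includes fatal TEAEs whatever the timing of death.

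The 40% case may be the least common. The Week 12 window closes at the first injection from the up-titration kit (SAP 2.5.3), so Weeks 8 and 12 both reflect the starting dose, and a first low value at Week 12 needs a Week 8 value that was above the threshold or missing. The documents give no distribution of first low values.

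Finally, little may be lost in absolute terms. If 28 to 84 of about 280 alirocumab patients qualified and the true risk of a follow-up-ending event were 1–2% (all assumed), the loss is between 28 × 0.01 × 0.17 ≈ 0.05 and 84 × 0.02 × 0.40 ≈ 0.7 events. Every such event remains in the overall TEAE tables and the SAE and death listings. This limits the importance of the point but does not remove the flaw in the subgroup rates.

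**Conclusion.** The point holds for events that end follow-up: the subgroup tables understate them whenever they fall between the two low values. The 17%, 40% and 33% shares assume scheduled visit days and a completer's Day 225; the rate ratios also assume a constant hazard. For events that only end treatment, loss is probable rather than certain, and the 8%, 30% and 17% rest on a carry-over that the SAP states for another lipid and another analysis. The patient-year problem depends on a literal reading of the general definition, but nothing in the SAP overrides that reading for these subgroups. The analysis is descriptive and conditional, with no test or decision attached, so the matter is one of fair reporting of a safety subgroup.

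**What to change.** In SAP 2.4.5.1, for these subgroups only:

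1. Start both TEAE counting and person-time on the day of the second, qualifying value.
2. Keep the count from the first low value as a supportive table, with person-time started at that value, and note that it still contains the event-free gap.
3. List patients with one low value and no later LDL-C sample, together with their TEAEs. The landmark alone does not recover them, since they are outside the subgroup under either rule.

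The listing will not show a patient who stopped treatment and whose next value was above the threshold; that event remains visible in the overall table of TEAEs leading to discontinuation.

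The cost is a wording change, one derivation date and one listing. For a completer, follow-up in the main subgroup table falls from 168, 140 or 84 days to 140, 84 or 56 days. Ordinary TEAEs in the gap move to the supportive table, so no event now reported is lost, but the main table will hold fewer events.
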